5.2 Exclusion criteria

Trial-wide:

- Life expectancy less than 12 months
- Are too cognitively impaired to provide informed consent/assent and/or complete study protocol
- Are institutionalized or too ill to participate (i.e. mental or nursing home facility or incarcerated)
- Have a history of allogeneic stem cell transplant or liver transplant
- People with prior clinical pharmacogenetic test results for genes relevant for the study in which they will enroll (*CYP2D6* for the pain studies and *CYP2D6* or *CYP2C19* for depression) or already enrolled in an ADOPT PGx trial
- Any other medical, behavioral, or developmental condition that in the opinion of the investigator may confound study data/assessments

Acute Pain

- Receiving chronic opioid therapy, defined as use of opioids on most days for >3 months

Chronic Pain

- Plan to move out of the area within 6 months of enrollment
- Undergoing treatment for an active cancer diagnosis
- Currently taking daily opioids other than tramadol, codeine or hydrocodone for treatment of pain
- Using a pain pump

Depression

- Plan to move out of the area within 6 months of enrollment
- Have active psychosis or diagnosis of a psychotic disorder (schizophrenia, schizoaffective disorder, delusional disorder, psychotic depression, substance induced psychosis, schizopreniform disorder) Have dementia or other neurocognitive disorders due to any cause, such as Alzheimer's disease, vascular/subcortical, lewy body, frontotemporal lobar degeneration
- Have cognitive developmental delay and/or cognitive disability, including autism spectrum disorders (Note: ADHD is not an exclusion criteria)
- Has a seizure disorder
- Have bipolar disorder

6. RECRUITMENT AND ENROLLMENT PROCEDURES

Outlined below are **suggested strategies** for recruitment and enrollment. It is anticipated that each site will need to optimize the strategies that work best for the clinic and patient population and are in accordance with local regulations and procedures. Strategies utilized will be documented for each recruiting site (see MOP for details). Sites shall maintain local recruitment logs per local policies and share aggregated data with the CC.

6.1 Provider Recruitment and Assent

Acute Pain: Providers with a predominant use of codeine, tramadol, and hydrocodone for pain control before and during the 10-day primary endpoint may be approached by qualified study personnel. Providers will be notified per site institutional guidelines that their patients may be contacted by study site recruiters to participate. Surgical procedures where there is persistent pain at the 10-day primary endpoint should be prioritized for inclusion in the study.

Chronic Pain: Primary care providers, pain clinic providers, and/or anesthesiologists specializing in pain control who treat patients meeting eligibility criteria will be identified, and may be approached by qualified study personnel. Providers will be notified per site institutional guidelines that their patients may be contacted by study site recruiters to participate.

Depression: Primary care providers and psychiatric providers who manage the care of eligible patients will be identified, and may be approached by qualified study personnel, and given the opportunity to participate as a study provider. Providers will be notified per site institutional guidelines that their patients may be contacted by study site recruiters to participate.

6.2 Participant Consent Process

Pre-screened participants that meet the inclusion criteria will be asked to provide an informed consent/assent.

Original informed consent documents will be maintained at the site. Copies of the signed informed consent will be given to the participant. The consenting process can be remote, via a phone or electronically if approved by the reviewing IRB.

6.3 Participant Discontinuation/Withdrawal from the Study

Participants may stop participating and withdraw from the study at any time. All information and data collected up until that point will be used in the study.

If a participant wishes to withdraw consent, they should contact study staff. A participant may also revoke HIPAA authorization and must provide the revocation in writing. Study staff may attempt to obtain a reason for withdrawal from the participant and record it in the study database.

In the acute pain trial, the principal investigators or clinical site investigators may withdraw a participant from the study for any of these reasons:

- Participant does not have the surgery within 12 months of study enrollment
- Participant has the surgery at a healthcare system that is different from where the participant enrolled
- Participant's surgery is scheduled for a date after the close of the enrollment period for that clinical site
- Participant is unable to have the surgery for other medical reasons

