4.2 Blinding

ADOPT PGx randomization assignments will not be blinded to the participants or their providers but will be masked to the UF call center personnel who may be administering some of the participants follow-up surveys. Due to the nature of the intervention, it is impossible to completely mask participants and providers from the pharmacogenetic testing and return of results, hence participants, providers, and local study personnel will not be blinded. While the UF call center personnel administering follow-up surveys will be masked from the results and randomization, study-arm specific questions in the final (6 month) survey may reveal study arm randomization. Additionally, participants may volunteer to reveal their randomization or PGx testing results. If the randomization or phenotype is revealed to the call center, prior to administering the 6 month surveys, it will be documented in the database.

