5. STUDY POPULATION

5.1 Inclusion Criteria

Acute Pain

- Age \geq 8 years
- English speaking or Spanish speaking
- Elective/planned surgery types with planned or anticipated to be treated with tramadol, hydrocodone, or codeine pain management at an enrolling site, which may include orthopedic surgeries(e.g. arthroplasty, spine, etc.), open abdominal surgery, or cardiothoracic surgery and others

Chronic Pain

- Age \geq 18 years
- English speaking or Spanish speaking
- Seen at primary care clinics at an enrolling site (such as, but not limited to, Internal Medicine, Family Medicine, Pediatrics) or seen in pain-relevant specialty clinics
- History of pain for at least the last 3 months
- Currently treated or being considered for treatment with tramadol, hydrocodone, or codeine to improve pain management

Depression

Age \geq 8 years

- English speaking or Spanish speaking
- Patients followed at psychiatry clinics or primary care clinics at an enrolling site (such as, but not limited to, Internal Medicine, Family Medicine, or Pediatrics)
- Documentation of depression and/or provider report of depression
- Evidence of depressive symptoms for at least 3 months based on patient interview or documentation in electronic health records
- Recent initiation of SSRI therapy, recent revised SSRI therapy, or anticipate need for revised or new SSRI therapy per health care provider

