10. STATISTICAL ANALYSIS PLAN AND SAMPLE SIZE

10.1 Sample Size Determination

All trials power analyses are based on a modified intent to treat analysis, comparing the subset of intervention participants with have an actionable phenotype to the subset of control participants with an actionable phenotype. Effect sizes used to estimate power are based on prior studies of pain and depression pharmacogenetic testing and described below for each trial and shown in Table 8. Several steps were taken to generate a conservative sample size estimate. First, the power requirement was set to 90%. Second, sample sizes are adjusted for a 10% drop-out (for which UF has data from several studies that this is a good estimate). Third, slightly smaller effect sizes than what was observed in prior studies was used. Finally, sample size calculations are based on an alpha of 0.049, to allow one interim analysis with an alpha of 0.001 in each study.

Due to the study design and the delay in the control arm to obtaining the genotyping results required determine the actionable phenotype subgroup assignment, it is not feasible to directly monitor the number of randomized participants in the actionable subgroup for the enrollment stopping rule. Alternatively, the observed trial specific actionable phenotype percentages and the corresponding trial specific total enrollment targets will be used to identify when enrollment can conclude for a fully powered mITT study.

Acute Pain

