In the University of Florida's pilot acute pain study, the difference between study arms in SIA score was -38.55 with a SD of 93.5, for a standardized effect size of 0.412. Assuming a reduced standardized effect size of 0.375, 304 participants with an actionable phenotype per group, 152 from the intervention arm and 152 from control arm, are required to achieve 90% power for a two-sided two-sample t-test. Preliminary data from the University of Florida's acute pain study indicates the proportion of participants with an actionable phenotype, genotypic or pheno-converted CYP2D6 IM or PM, will be approximately 18%. After adjusting for the subset anticipated to have an actionable phenotype, 845 participants completing all assessments, per group, are required to achieve 90% power in the sub-group analysis (1678 total). Assuming 10% drop out or lost to follow-up and 7% of participants not going on to surgery, a total of 2020 randomized participants is required to sufficiently power this study. Factoring in variability in the proportion that are IMs or PMs (15% to 24%), 1516 to 2424 randomized subjects would be need to achieve 90% power in the mITT analysis.

Chronic Pain: In the University of Florida's prior chronic pain study, the difference between study arms in composite pain score was 0.6 with a SD of 1.4, for a standardized effect size of 0.43. The same effect size was observed when assessing 3-month changes in pain scores. Assuming a standardized effect size of 0.40, 268 participants within the specified subgroup, 134 from the intervention arm and 134 from control arm, are required to achieve 90% power for a two-sided two-sample t-test. Preliminary data indicate the proportion of participants with an actionable phenotype will be 30-35%; 10-15% of participants with an actionable genotype-based phenotype (CYP2D6 IM or PM) and an additional 20% with a pheno-converted PM/IM based on drug-drug-gene interactions. After adjusting for the subset anticipated to have an actionable phenotype, 447 participants completing all assessments, per group, are required to achieve 90% power in the sub-group analysis (894 total). Assuming 10% drop out or lost to follow-up, a total of 994 randomized participants is required to sufficiently power this study. Factoring in variability of the proportion of randomized population that are IMs or PMs (24-33%), 906 to 1244 randomized subjects would be need to achieve 90% power in the mITT analysis.

Depression:

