10.4 Analysis of the Primary Endpoint

Acute Pain

To determine the effect of genotype-guided drug therapy on pain control in acute pain participants, we will conduct a subset analysis comparing SIA scores at 10-days post-surgery in the Intervention group subset with CYP2D6 IM or PM phenotypes to the Control group subset with CYP2D6 IM or PM phenotypes. Participants that have other CYP2D6 phenotypes will not be included. The 10-day post-surgery SIA scores of the Intervention CYP2D6 IM/PM group will be compared to the 10-day post-surgery SIA scores of the Control CYP2D6 IM/PM group using a two-sided two-sample t-test or Mann Whitney test, as appropriate, with a type 1 error of 0.049. This primary analysis will be conducted as a modified intent-to-treat analysis, with participants analyzed and endpoints attributed according to the treatment arm to which the participants were randomized, regardless of subsequent crossover or post-randomization medical care.

Chronic Pain

To determine the effect of genotype-guided drug therapy on pain control in chronic pain participants, we will conduct a subset analysis comparing change in pain intensity score from baseline to 3-month follow-up in the Intervention group subset with CYP2D6 IM or PM phenotypes to the Control group subset with CYP2D6 IM or PM phenotypes. Participants that have other CYP2D6 phenotypes will not be included. The baseline to 3-month change in pain intensity of the Intervention CYP2D6 IM/PM group will be compared to the baseline to 3-month change in pain intensity of the Control CYP2D6 IM/PM group using a two-sided two-sample t-test or Mann Whitney test, as appropriate, with a type 1 error of 0.049. This primary analysis will be conducted according to modified intent-to-treat design, with participants analyzed and endpoints attributed according to the treatment arm to which the participants were randomized, regardless of subsequent crossover or post-randomization medical care.

Depression

To determine the effect of genotype-guided drug therapy on depression symptoms in depression

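### Acute Pain, section 6.3: unblinded investigators may withdraw randomised participants because of where or when surgery takes place, although the day-10 primary outcome can still be collected remotely

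*Combined protocol and SAP*

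**What the plan says.** For the acute-pain trial, section 6.3 lists reasons for which principal or site investigators may withdraw a participant. Two of them concern participants who do go on to surgery. The first is about place: "Participant has the surgery at a healthcare system that is different from where the participant enrolled". The other, next in the list, is about timing and applies when the "Participant's surgery is scheduled for a date after the close of the enrollment period for that clinical site".

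The permission is discretionary. Randomisation follows consent and DNA sample collection (sections 4.1 and 7.4) and baseline surveys are completed before surgery (section 7.2), so these events fall after allocation. Section 4.2 states that "participants, providers, and local study personnel will not be blinded".

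The inclusion criterion in section 5.1 is "Elective/planned surgery types with planned or anticipated to be treated with tramadol, hydrocodone, or codeine pain management at an enrolling site". It refers to place but sets no limit on the surgery date.

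On analysis, section 10.3 defines the acute-pain population as randomised participants with an actionable CYP2D6 phenotype and makes no exception for withdrawal. Section 10.4 analyses them in their randomised arm "regardless of subsequent crossover or post-randomization medical care". Section 10.8 multiply imputes all missing values except those due to death. Section 7.5 processes control samples only after the control participant has completed the 6-month assessment.

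**The concern.** A participant who is operated on elsewhere, or later than the site expected, is still a randomised participant with a day-10 outcome. If an investigator who knows the arm may end that person's participation, selection enters the primary comparison after randomisation.

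Three things are at stake:

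- **Lost outcome.** Withdrawal before day 10 replaces a measurement that could have been made with an imputed value. The imputation would draw mainly on participants operated on at the enrolling system, whose record holds the result and, where implemented, the alert. If the intervention reaches fewer of those operated on elsewhere, this overstates the effect of the strategy as randomised.
- **Arm-aware choice.** For surgery elsewhere there is a plausible reason to withdraw intervention participants in particular, because the operating team may not see the result. No such reason applies to controls.
- **Unequal identification of the mITT set.** Intervention samples are genotyped without waiting for follow-up. A withdrawn control may never complete the assessment that triggers genotyping, and the documents do not say whether that sample is processed. Actionable status could stay unknown for withdrawn controls while it is known for withdrawn intervention participants.

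**Working it through.** **1. Is the day-10 outcome obtainable?** Section 11.2 builds the SIA score from ranked pain and ranked opioid usage. Pain is a participant survey item (section 7.3), and morphine equivalents are calculated from the opioid usage survey (section 11.2). Surveys may be completed in person, by phone, web link, text or email (section 6.4), and a central call centre may collect them (section 7.3). Neither component depends on the hospital of surgery.

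**2. Is there time after enrolment closes?** Section 8.2 allows EHR collection to about 12 months after the last randomisation, to cover completion of 6-month follow-up. Since acute-pain follow-up starts at surgery, that leaves room for surgery up to about 12 − 6 = 6 months after the last randomisation. A day-10 survey needs less.

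**3. Reproduce the planned size (section 10.1).** Inputs: "sample size calculations are based on an alpha of 0.049", 90% power, and "Assuming a reduced standardized effect size of 0.375"; also 18% actionable, 10% drop-out and 7% without surgery.

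- Two-sample t-test: n = 151.2, rounded up to 152 per arm; power at 152 is 90.1%.
- Completers: 152 / 0.18 = 844.4, so 845 per arm and 1690 in total.
- Randomised: 1690 / (0.90 × 0.93) = 2019; the plan states 2020.

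The plan's figures reproduce. The 7% covers only participants who do not go on to surgery.

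**4. Effect on power.** The documents give no rate for these withdrawals, so w is an assumption, treated as loss beyond the plan's allowances. Starting point: 2020 × 0.18 × 0.90 × 0.93 / 2 = 152.2 analysed per arm. Lost: n = 152.2 × (1 − w) with effect 0.375. Retained, worst case of zero effect in these participants: n = 152.2 with effect 0.375 × (1 − w).

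| w | n per arm if lost | Power if lost | Power if retained, zero effect in them |
|---|---|---|---|
| 0 | 152.2 | 90.2% | 90.2% |
| 2% | 149.1 | 89.6% | 89.0% |
| 5% | 144.6 | 88.7% | 87.1% |
| 10% | 136.9 | 86.9% | 83.3% |

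The loss is small, and in the worst case retention does not recover it.

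**5. Effect on bias.** Suppose a fraction w of one arm only is withdrawn, their mean lies s SD from that arm's mean, and the estimate rests on the rest. The arm mean then shifts by w × s / (1 − w). Both w and s are assumptions.

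| w | s = 0.25 SD | s = 0.5 SD |
|---|---|---|
| 2% | 0.005 SD (1.4% of 0.375) | 0.010 SD (2.7%) |
| 5% | 0.013 SD (3.5%) | 0.026 SD (7.0%) |
| 10% | 0.028 SD (7.4%) | 0.056 SD (14.8%) |

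With the pilot SD of 93.5, the extremes are 0.005 × 93.5 ≈ 0.5 and 0.056 × 93.5 ≈ 5.2 SIA points.

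**The case against.** Several points on the other side stand.

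- **Place is addressed at entry.** A reader might infer that eligibility has no check on where surgery happens. That is too strong, because section 5.1 refers to an enrolling site. The wording does not clearly require the participant's own enrolling system, and no entry criterion can prevent a later change of hospital.
- **No explicit contradiction of the mITT rule.** A reader might infer that section 6.3 removes these participants from the analysis or discards their data. The documents do not say so. Withdrawal is permitted, not required; section 6.3 says data collected up to a withdrawal are used; section 10.8 imputes the rest. Details are deferred to separate trial SAPs. What remains is a tension: an obtainable outcome stops being collected, and the control genotyping trigger may not be reached.
- **The allowances may absorb some loss.** The 10% drop-out term could reasonably include investigator withdrawals, and the synopsis says targets may change with missing data. Treating every withdrawal as extra loss is an upper reading.
- **Power does not argue for retention.** Step 4 concedes this. The case rests on validity.
- **The two reasons differ.** The enrolment-close reason turns on scheduling, and there is no evident arm-specific motive for it. Some day-10 surveys might fall after study follow-up ends. Deleting that reason outright is not justified.

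The documents give no evidence that arm-dependent withdrawal has occurred. The point is that the wording allows it.

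**Conclusion.** The concern holds in a limited form. Section 6.3 permits arm-aware withdrawal, after randomisation, of participants who do have surgery and whose day-10 SIA score could still be collected by survey. That sits badly with the as-randomised intent of sections 10.3 and 10.4, and through section 7.5 it could make identification of the mITT set depend on arm.

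The size cannot be fixed from the documents, since no withdrawal rate is given. Under assumed losses of 2% to 10%, power is 89.6% to 86.9% against about 90% planned, a minor effect. Under the further assumptions that withdrawal is confined to one arm and those withdrawn differ by 0.25 to 0.5 SD, bias is 0.005 to 0.056 SD, or 1% to 15% of the planning effect. That calculation does not include any differential loss of controls through missing genotypes. The change is worth making because it is cheap and protects the randomised comparison.

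**What to change.** In section 6.3 (Acute Pain):

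1. Delete surgery at a different health system as a reason for withdrawal from the study.
2. Limit the enrolment-close reason to cases where the day-10 survey cannot be collected before study follow-up ends.
3. State that these participants continue the surveys through the call centre or web link and stay in the mITT set as randomised.
4. State that, for any control who is withdrawn, the stored sample is genotyped where consent allows, so that actionable status is established in both arms.
5. Report any investigator withdrawals by arm and reason.

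Cross-refer to this text from sections 7.5, 10.3, 10.4 and 10.8.

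If enrolment is still open, clarify in section 5.1 that surgery is planned at the enrolling health system. Also reconcile the 12-month window to surgery in section 6.3 with the synopsis, which gives participation as up to one year from consent to end of follow-up: 12 months to surgery plus 6 months of follow-up is 18 months. If enrolment has closed, the changes to section 6.3 and its cross-references are enough.

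Cost: protocol wording, a few more remote surveys, genotyping of a few control samples, and possibly some dilution of the estimated effect if the intervention does not reach those operated on elsewhere. That dilution is part of the effect of the strategy as randomised.

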6.4 Lost to Follow-Up

Participant status of lost to follow-up will be minimized and retention maximized through various mechanisms to collect study survey responses. The following options will be available: in person, via phone, or a web-based link, text or email. Study staff should confirm the best contact information for the participant at each study encounter.

Additionally, data collected from the EHR and Medicare and Medicaid claims data (see Section 9 for details) will be robust to missing data due to participants that are lost to follow up.

6.5 Risk

The potential risks described below are minimal and reasonable in relation to the potential benefit for genotype-guided therapy to improve the management of pain and depression and reduce the pain and depression burden to society.

Blood Draw

The risks of a blood draw include pain, bruising, and the slight possibility of infection at the place of needle insertion. Some people feel dizzy or may faint during or after a blood draw.

Off FDA label use of antidepressants

In the depression trial, specifically in the pediatric population, the standard practice of medicine may include use of antidepressants that are currently not FDA approved to treat depression in pediatrics. Use of drugs not labeled for use in pediatrics, but prescribed by their treating physician, is not a risk due to study participation.

Prescription Changes

It is possible that the PGx-PGx-recommended drug therapy change may lead to worse pain control or worse control of depression symptoms, though the likelihood is that is no different than with the usual trial and error approach typically used for defining pain management or antidepressant therapy. Pharmacogenetic information is expected to lead to safer and more effective drug therapy, and the ultimate prescribing decision in this study will be left to the physicians. Thus, there are no anticipated risks with basing therapy on pharmacogenetic test results and our preliminary data support a clinical benefit, not risk.

Genetic Information Privacy

The risks of study participation are primarily those related to genetic studies, including risks related to confidentiality surrounding the genetic information and the chance that the genetic information could in some way expose the participant to increased risk regarding employment or that future life, health, disability or long-term care insurance providers could potentially use this genetic information to deny, limit or raise rates for insurance coverage. The Genetic Information Nondiscrimination Act (GINA) makes it illegal for health insurance companies, group health plans, and most employers to discriminate based on genetic information, but other insurers may still use genetic information to discriminate. The pharmacogenetics examples included in our study are only known to be associated with drug response, which is unlikely to lead to insurance discrimination as long as effective, alternative therapies are available, as they are for all gene-drug pairs included in this study.

